8.5.2 Secondary analysis methods

8.5.2.1 Analysis methods for secondary efficacy variables

Key secondary efficacy endpoints in this study are:

- Change from baseline in pre-dose/pre-bronchodilator FEV₁ at Week 56
- Change from baseline in SGRQ total score at Week 56

Other secondary efficacy endpoints include

- Proportion of subjects with ≥ 1 COPD exacerbation

- Time to the first COPD exacerbation
- Proportion of subjects with ≥ 4 -point decrease (improvement) in SGRQ total score at Week 56
- Annual rate of COPD exacerbations that are associated with an emergency room visit or a hospitalization
- Annual rate of hospitalizations, annual rate of hospitalizations and emergency room visits combined, annual rate of unscheduled outpatient visits including unscheduled visits to study centres and all unscheduled healthcare encounters due to COPD
- Rescue medication use (average puffs/day)
- Number of nights with awakening due to COPD and requiring rescue medication
- Change from baseline in E-RS total score and domain scores at Week 56
- Area under the curve (AUC) of E-RS total score
- BDI/TDI
- CAT
- EXACT-PRO

All the secondary efficacy endpoints will be analyzed in subjects with baseline blood eosinophil counts $\geq 220/\mu\text{L}$. In addition, the two key secondary endpoints will also be summarized in subjects with baseline blood eosinophil counts $< 220/\mu\text{L}$, $< 150/\mu\text{L}$, $150-219/\mu\text{L}$, $220-299/\mu\text{L}$, $300-449/\mu\text{L}$, and $\geq 450/\mu\text{L}$ separately for descriptive purpose only.

Change from baseline in pre-dose/pre-bronchodilator FEV_1 at Week 56 will be compared between each of the three benralizumab dose groups and placebo using a repeated measures analysis on subjects with a baseline pre-dose/pre-bronchodilator FEV_1 and at least one post-randomisation pre-dose/pre-bronchodilator FEV_1 in the full analysis set. The dependent variable will be the change from baseline in pre-bronchodilator FEV_1 at post-baseline protocol-specified visits (up to the EOT visit). Treatment group will be fitted as the explanatory variable, and eosinophil cohort ($220-299/\mu\text{L}$ or $\geq 300/\mu\text{L}$), country, background therapy (ICS/LABA, LABA/LAMA, or ICS/LABA/LAMA), visit, the interaction between visit and treatment and baseline pre-bronchodilator FEV_1 will be fitted as covariates. Visit will be fitted as a categorical variable, and the variance-covariance matrix will be assumed to be unstructured. If the procedure does not converge then a compound symmetric variance-covariance matrix will be used instead. The model is:

*Change in FEV₁ = Treatment group + eosinophil cohort (220-299/ μ L or \geq 300/ μ L) + baseline FEV₁ + country + background therapy (ICS/LABA, LABA/LAMA, or ICS/LABA/LAMA) + visit + treatment*visit*

Change from baseline in SGRQ total score and three domain scores (symptoms, activity, and impacts) at Week 56 will be analyzed separately using a similar model as the above model for change from baseline in pre-dose/pre-bronchodilator FEV₁.

Proportion of subjects with \geq 4-point decrease (improvement) in SGRQ total score at Week 56 in each of the three benralizumab dose groups will be compared with the proportion in the placebo group using a Cochran–Mantel–Haenszel test controlling for eosinophil cohort (220-299/ μ L or \geq 300/ μ L), country, and background therapy (ICS/LABA, LABA/LAMA, or ICS/LABA/LAMA). Cumulative distribution function of absolute changes in SGRQ total score at week 56 will be plotted in a figure.

The proportion of subjects with \geq 1 COPD exacerbation during the 56 weeks of treatment will be addressed as a supportive variable to the primary objective. The proportion in each of the three benralizumab dose groups will be compared with the proportion in the placebo group using a logistic regression model with eosinophil cohort (220-299/ μ L or \geq 300/ μ L), country, background therapy (ICS/LABA, LABA/LAMA, or ICS/LABA/LAMA), and number of exacerbations in the year before the study as covariates.

Time to first COPD exacerbation will be analyzed as another supportive efficacy variable to the primary objective to explore the extent to which treatment with benralizumab delays the time to first exacerbation compared with placebo. A Cox proportional hazard model will be fitted to data with the covariates of treatment, eosinophil cohort (220-299/ μ L or \geq 300/ μ L), country, background therapy (ICS/LABA, LABA/LAMA, or ICS/LABA/LAMA), and number of exacerbations in the year before the study.

Annual rate of COPD exacerbations that are associated with an emergency room visit or a hospitalization will be analyzed using a similar Negative binomial model as outlined for the primary efficacy variable in section 8.5.1.

Annual rates of hospitalizations, hospitalizations and emergency room visits combined, unscheduled outpatient visits including unscheduled visits to study centres as well as all unscheduled healthcare encounters due to COPD (hospitalizations, emergency room visits, and unscheduled outpatient visits including unscheduled visits to study centres) will be analyzed using Negative Binomial Models as outlined for the primary efficacy variable in section 8.5.1.

The number of nights with awakening due to COPD and requiring rescue medication will be analyzed as the response variable by fitting a repeated measures model to data. Treatment group will be fitted as the explanatory variable, and eosinophil cohort (220-299/ μ L or \geq 300/ μ L), country, baseline value and background therapy (ICS/LABA, LABA/LAMA, or ICS/LABA/LAMA) will be fitted as covariates. Rescue medication use (average puffs/day) will be analyzed using a similar model.

Change from baseline in E-RS total score and domain scores at Week 56 will be analyzed separately using a similar model as the model for change from baseline in pre-dose/pre-bronchodilator FEV₁. AUC of E-RS total score will be analyzed by fitting an ANCOVA model with treatment, eosinophil cohort (220-299/ μ L or \geq 300/ μ L), country, baseline value, and background therapy (ICS/LABA, LABA/LAMA, or ICS/LABA/LAMA) as covariates.

The BDI/TDI, EXACT-PRO, and CAT will be summarized by treatment and visit.

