To evaluate the effect of three doses of benralizumab on COPD exacerbations in subjects with moderate to very severe COPD	
Annual COPD exacerbation rate, where a COPD exacerbation is defined by symptomatic worsening of COPD requiring:
 
 • Use of systemic corticosteroids for at least 3 days; a single depot injectable dose of corticosteroids will be considered equivalent to a 3-day course of systemic corticosteroids; and/or • Use of antibiotics; and/or • An inpatient hospitalization or death due to COPD

(b) Secondary Objectives

Secondary Objective:	Outcome Measure:
To evaluate the effect of three doses of benralizumab on health status/health-related quality of life	
 • St. George's Respiratory Questionnaire (SGRQ)* • COPD assessment tool (CAT)
To evaluate the effect of three doses of benralizumab on pulmonary function	Pre-dose/pre-bronchodilator Forced expiratory volume in one second (FEV ₁)* at the study centre
To evaluate the effect of three doses of benralizumab on respiratory symptoms	
 • Baseline/Transitional Dyspnea Index (BDI/TDI) • Exacerbations of Chronic Pulmonary Disease Tool – Respiratory Symptoms (E-RS)
To evaluate the effect of three doses of benralizumab on nocturnal awakenings	Number of nights with awakening due to COPD

Secondary Objective:	Outcome Measure:
To evaluate the effect of three doses of benralizumab on rescue medication use	Total rescue medication use (average puffs/day)
To evaluate the effect of three doses of benralizumab on the severity, frequency and duration of EXACT-PRO defined events.	Exacerbations of Chronic Pulmonary Disease Tool – Patient-reported Outcome (EXACT-PRO)
To evaluate the effect of three doses of benralizumab on other parameters associated with COPD exacerbations	Time to first COPD exacerbation and proportion of subjects with ≥ 1 COPD exacerbation
To evaluate the effect of three doses of benralizumab on COPD exacerbations involving emergency room visits and hospitalizations	Annual rate of COPD exacerbations that are associated with an emergency room visit or a hospitalization

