2.2 Secondary objectives

Secondary Objective:	Outcome Measure:
To evaluate the effect of three doses of benralizumab on health status/health-related quality of life	
 • SGRQ* • CAT
To evaluate the effect of three doses of benralizumab on pulmonary function	Pre-dose/pre-bronchodilator FEV ₁ * at the study centre
To evaluate the effect of three doses of benralizumab on respiratory symptoms	
 • BDI/TDI • E-RS
To evaluate the effect of three doses of benralizumab on rescue medication use	Total rescue medication use (average puffs/day)
To evaluate the effect of three doses of benralizumab on nocturnal awakenings	Number of nights with awakening due to COPD

Secondary Objective:	Outcome Measure:
To evaluate the effect of three doses of benralizumab on the severity, frequency and duration of EXACT-PRO defined events	EXACT-PRO
To evaluate the effect of three doses of benralizumab on other parameters associated with COPD exacerbations	Time to first COPD exacerbation and proportion of subjects with ≥ 1 COPD exacerbation
To evaluate the effect of three doses of benralizumab on COPD exacerbations involving emergency room visits and hospitalizations	Annual rate of COPD exacerbations that are associated with an emergency room visit or a hospitalization
To evaluate the effect of three doses of benralizumab on health care resource utilization due to COPD	Annual rate of hospitalizations due to COPD; annual rate of hospitalizations and emergency department visits combined due to COPD; annual rate of unscheduled outpatient visits including unscheduled visits to study centres due to COPD; and annual rate of unscheduled healthcare encounters due to COPD
To evaluate the pharmacokinetics and immunogenicity of three doses of benralizumab	
 • PK parameters • Anti-drug antibodies (ADA)

* Key secondary efficacy endpoints

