5.1.3.8 Rescue Medication Use

Rescue medication usage including reliever inhaler and nebulizer use will be captured twice daily. Inhaler usage will be reported as the number of puffs in a given period whereas nebulizer use will be reported as the number of times. Rescue medication usage at night will be assessed in the morning and rescue medication used during the day will be assessed in the evening.

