5.1.3.9 Nocturnal Awakenings

Subjects will be asked to report the occurrence of nocturnal awakenings due to COPD symptoms each morning using the ePRO device. A single question with yes/no response options will be used.

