Time to first COPD exacerbation will be analyzed as another supportive efficacy variable to the primary objective to explore the extent to which treatment with benralizumab delays the time to first exacerbation compared with placebo. A Cox proportional hazard model will be fitted to data with the covariates of treatment, **eosinophil cohort (220-299/ μ L or \geq 300/ μ L)**, country, background therapy (ICS/LABA, LABA/LAMA, or ICS/LABA/LAMA), and number of exacerbations in the year before the study.

...

The number of nights with awakening due to COPD and requiring rescue medication will be analyzed as the response variable by fitting a **repeated measures** model to data. Treatment group will be fitted as the explanatory variable, and **eosinophil cohort (220-299/ μ L or \geq 300/ μ L)**, country, baseline value and background therapy (ICS/LABA, LABA/LAMA, or ICS/LABA/LAMA) will be fitted as covariates. Rescue medication use (average puffs/day) will be analyzed using a similar model.

Change from baseline in E-RS total score and domain scores at Week 56 will be analyzed separately using a similar model as the model for change from baseline in pre dose/prebronchodilator FEV₁. AUC of E-RS total score will be analyzed by fitting an ANCOVA model with treatment, **eosinophil cohort (220-299/ μ L or \geq 300/ μ L)**, country, baseline value, and background therapy (ICS/LABA, LABA/LAMA, or ICS/LABA/LAMA) as covariates.

Reason for Amendment:

This change reflects 1) the new eosinophil boundary of $\geq 220/\mu\text{L}$ for all secondary efficacy endpoints, 2) the inclusion of an additional covariate – eosinophil cohort ($220\text{-}299/\mu\text{L}$ or $\geq 300/\mu\text{L}$) – in the statistical analysis models, and 3) the update of ANCOVA analysis to repeated measures analysis for all continuous endpoint analyses across time (consistent with the SAP).

Persons who initiated the Amendment:

Redacted, Global Product Statistician Delegate

Section of protocol affected:

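### The nocturnal-awakening endpoint is declared without a rescue-medication condition but listed and modelled with one

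*Protocol*

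**What the plan says.** The synopsis (secondary objectives) and section 2.2 both set an objective on nocturnal awakenings and pair it with the outcome measure "Number of nights with awakening due to COPD". Neither attaches a rescue condition. Rescue use has its own row in the same tables: the objective is "To evaluate the effect of three doses of benralizumab on rescue medication use" and the measure is total use in average puffs per day.

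Section 5.1.3.9 describes the data collection: "Subjects will be asked to report the occurrence of nocturnal awakenings due to COPD symptoms each morning using the ePRO device". On the format it adds: "A single question with yes/no response options will be used". Section 5.1.3.8 treats rescue use as a separate diary entry: "Rescue medication usage at night will be assessed in the morning".

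Section 8.5.2.1 then lists, among the other secondary efficacy endpoints, "Number of nights with awakening due to COPD and requiring rescue medication". Later in the same section the model is specified for that variable: "The number of nights with awakening due to COPD and requiring rescue medication will be analyzed as the response variable". The model is a repeated measures model with treatment as the explanatory variable and with eosinophil cohort, country, baseline value and background therapy as covariates.

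**The concern.** The declared measure and the analysed measure are different variables. A night on which the subject woke because of COPD but took no reliever counts under section 2.2 and does not count under section 8.5.2.1. The only awakening endpoint that is listed, and the only one given a model, is the restricted one, so the measure attached to the objective has no described analysis.

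Two things are at stake.

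- **Interpretation.** The restricted count combines waking with reliever use. A treatment difference in it cannot be read as an effect on awakenings alone.
- **Pre-specification.** With two definitions standing in the same document, either could be reported as the planned one after the data are seen.

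**Working it through.** No figure in the protocol depends on this definition, so the check compares the texts and then considers what separates the two variables.

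**Where each definition stands in the current protocol**

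| Place | Rescue condition? |
|---|---|
| Synopsis, secondary objectives | No |
| Section 2.2 | No |
| Section 5.1.3.9 (diary item) | No |
| Section 8.5.2.1, endpoint list | Yes |
| Section 8.5.2.1, model | Yes |

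The outcome measure is therefore stated without the condition in 2 places and with it in 2 places. The number of places that reconcile them is 0. Section 8.4.3, which derives the patient-reported variables, does not cover awakenings and so does not settle the matter.

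**How the variables relate.** For subject *i* and night *j*, let *a* = 1 if the subject woke because of COPD, and *r* = 1 if the awakening required rescue medication; both are otherwise 0.

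- Declared count: A = Σ a
- Analysed count: R = Σ a·r

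Since r is 0 or 1, R ≤ A for every subject over any period. Within a treatment group, mean R = mean A × q, where q is the share of awakening nights that required rescue. For a dose versus placebo:

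R(dose)/R(placebo) = [A(dose)/A(placebo)] × [q(dose)/q(placebo)]

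The first factor is the effect on awakenings. The second is the effect on reliever use given an awakening. The analysed variable carries their product, so it isolates the first only if q is the same in both groups. The protocol gives no awakening rate, no night-time rescue rate and no value of q, so neither factor can be put into numbers.

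**Whether r is observed.** As sections 5.1.3.8 and 5.1.3.9 describe the diary, awakening is one yes/no item and night-time rescue use is a separate morning entry. No described item asks whether an awakening called for rescue. The restricted variable would have to be built from both being reported on the same morning, which shows that they happened on the same night but not that one led to the other.

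**Which definition is intended.** The documents do not settle this. The revised 8.5.2.1 text in Amendment 3 changed the model for this endpoint from ANCOVA to repeated measures, added the eosinophil cohort and kept the rescue condition, which could indicate that the narrower variable is meant. The outcome measure in the current synopsis and section 2.2, together with the diary item, points the other way.

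**The case against.** The strongest reply concerns weight and remedy; the difference in wording itself is not in dispute.

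- **Small consequence.** This is not a key secondary endpoint and it lies outside both gatekeeping procedures. Both diary items are collected daily, so either variable can still be derived. This stands, and it limits the importance of the point.
- **The SAP may resolve it.** Derivation detail does belong there, and its absence from the protocol is no fault. But the protocol has already stated two incompatible definitions, so an SAP that follows one must depart from the other.
- **The list in 8.5.2.1 is not worded as exhaustive.** That is true, and the protocol does not rule out an analysis of the unrestricted count. It describes none, however, and it names the restricted count as the response.
- **Overlap between objectives is not an error in itself.** This is fair: an awakening bad enough to need reliever is a legitimate, severity-qualified measure and is not the same as average puffs per day. The difficulty is that it is not the measure declared for this objective.
- **Preferring deletion is a judgement.** This also stands in part. Amendment 3 kept the condition, so the sponsor may intend the narrower variable, and the fix must allow for that.
- **The exact ePRO wording is not reproduced.** The statement that the diary does not link rescue use to an awakening therefore rests on how sections 5.1.3.8 and 5.1.3.9 describe the items.

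**Conclusion.** The contradiction is real and lies wholly in current protocol text. Section 8.5.2.1 analyses a subset of what the synopsis and section 2.2 declare, and nothing reconciles them. The size of the gap cannot be derived from the document; the only firm statement is that the restricted count cannot exceed the unrestricted one. The effect is confined to one non-key secondary endpoint. The primary analysis, type I error control and sample size are not touched. It should be corrected because the definition decides what is reported under the nocturnal-awakening objective. The conclusion that the texts conflict rests on no numerical assumption.

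**What to change.** Use one definition in the synopsis, section 2.2 and section 8.5.2.1.

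- **Preferred:** delete the last four words of "Number of nights with awakening due to COPD and requiring rescue medication" in the endpoint list of 8.5.2.1, and the same four words in the model sentence. This matches the declared outcome measure and the diary item. If the rescue-linked count is also wanted, list it separately as supportive. Define it as a night with awakening answered yes and any night-time rescue use, by inhaler or nebulizer, reported the same morning, and state that this is a proxy because the diary as described does not tie the rescue use to the awakening.
- **If only the narrower variable is intended:** amend the outcome measure in the synopsis and section 2.2 to match, and state the same proxy definition.

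The cost is an edit in two places either way, plus a short definition if the rescue-linked count is kept. Awakening and night-time rescue use are already recorded daily, so no new data are needed.

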The study will recruit approximately 2168 subjects randomised 1:1:1:1 to the treatment arms, stratified by country and blood eosinophil count ($\geq 300/\mu\text{L}$ and $< 300/\mu\text{L}$ strata). The subject recruitment will be capped at the study level for the cohorts with baseline eosinophil counts $< 220/\mu\text{L}$, 220-299/ μL , and $\geq 300/\mu\text{L}$ in order to keep predefined cohort sample size and approximately 2:1 ratio of subjects above and below the boundary of 220/ μL . Details of the estimated numbers of recruited subjects/arm in each cohort ($< 220/\mu\text{L}$, 220-299/ μL , $\geq 300/\mu\text{L}$) are described in the SAP.

The investigational product (IP) will be administered at the study centre every 4 weeks for the first 3 doses, and then every 8 weeks thereafter, the last dose will be given at week 48 and the last treatment evaluation will be performed at week 56.

After the initial enrolment period and confirmation of the entry criteria, subjects will proceed to the screening/run-in period for 3 weeks to allow adequate time for all of the eligibility criteria to be evaluated. Subjects who meet all the eligibility criteria will be randomised to a 56-week treatment period, with the last dose of benralizumab/placebo administered at week 48. The end of treatment (EOT) visit will occur at week 56. Subjects will be maintained on their currently prescribed maintenance therapies, from enrolment throughout the run-in and treatment period.

Final follow-up visit will be conducted at week 60. For discontinuation procedures refer to section 3.6.1.

Target subject population

Male and female subjects between 40 to 85 years of age inclusive, with a diagnosis of COPD, post-bronchodilator $FEV_1 > 20\%$ and $\leq 65\%$ of predicted normal value, Modified Medical Research Council (mMRC) score ≥ 1 , and history of ≥ 2 moderate COPD exacerbations (i.e. treated with systemic steroids and/or antibiotics) or ≥ 1 severe exacerbation (i.e. requiring COPD related hospitalization) in the previous year, willing to provide informed consent and requiring maintenance treatment with double (ICS/LABA, LABA/LAMA) or triple (ICS/LABA/LAMA) therapy.

Investigational product, dosage and mode of administration

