3.6.1 Procedures for discontinuation of a subject from IP

Subjects who prematurely discontinue treatment should return to the study centre and complete the procedures described for the EOT 12 weeks (± 7 days) after the last dose of IP.

It is highly recommended that all study procedures, including any scheduled visits and ePRO completion, are continued till EOT visit, if possible. The subject will bring the ePRO device to the EOT visit.

At EOT visit the subject will be given two options on how to be followed up:

- The subject should be encouraged to return for all regular clinic and phone call visits until he/she completes a total of 56 weeks in the study. At week 56 all the procedures described for Visit 19 are to be conducted
- If the subject cannot comply or does not wish to comply with the option above, he/she will be offered to be followed up on a monthly basis via phone calls while continuing eDiary completion, until the subject completes 56 weeks in the study. No further procedures will be performed. The subject's decision needs to be documented and the specific section in the ICF addendum needs to be signed.

[figure not shown]
The key elements to be collected are AEs/SAEs, changes in concomitant medications, smoking status and COPD exacerbation information.

The Investigator will be instructed to force data transfer from the ePRO device on the day of EOT visit and then to redispense the device to subject. ePRO alerts will still be in place to notify both the subject and the study center of a potential symptom worsening event (see section 5.1.3.7). The subject will be asked to return the ePRO device to the study centre after the subject completes participation in the study (week 56).

- If the subject refuses the two previous options, he/she will need to sign the specific withdrawal of consent portion of the ICF addendum and return all study materials to the study centre.

AstraZeneca will continue to provide maintenance and rescue medications up to 56 weeks from the time of randomisation (see section 3.5.1) unless the patient withdraws consent. It is the Investigator's responsibility to fully evaluate the patient upon discontinuation or withdrawal to ensure that the patient receives appropriate treatment according to his/her clinical status/ condition.

Figure 2 Premature IP discontinuation

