^f In case of anaphylaxis additional samples will be taken (see section 6.9)

^g Phone follow-up applicable for subjects that discontinue from IP. Every 4 weeks (± 7 days) after the EOT visit up to week 56 as per the study plan.

^h Unscheduled visits may be initiated as needed, and additional assessments performed at these visits, at the discretion of the Investigator

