8.4 Variables for analyses

8.4.1 Calculation or derivation of efficacy variables

All efficacy objectives will be evaluated for the 56-week double-blind treatment period, defined as the period after administration of randomised investigational product at Visit 4 and the EOT at Visit 19, inclusive.

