8.4.1.4 Forced expiratory volume in 1 second

The change from baseline to each of the post-randomisation visits (post Visit 4) up to and including the end of 56-week double-blind treatment visit (Visit 19) will be used as secondary efficacy variables. The pre-bronchodilator measurement recorded at Visit 4 will be used as baseline FEV₁. If the Visit 4 pre-bronchodilator measurement is missing, the last non-missing pre-bronchodilator value before Visit 4 will be used as baseline instead.

8.4.1.5 Annual rate of COPD exacerbations that are associated with an emergency room visit or a hospitalization

The annual rate of COPD exacerbations that are associated with an emergency room visit or a hospitalization will be a secondary efficacy variable.

In the statistical analysis, the number of COPD exacerbations that are associated with an emergency room visit or a hospitalization experienced by a subject during the 56-week double-blind treatment period will be used as response variable, and the logarithm of the subject's corresponding follow-up time will be used as an offset in the analysis to adjust for subjects having different exposure times during which the events occur.

Maximum follow-up time is approximately 56 weeks, and the follow-up time is derived as described in section [8.4.1.1](#).

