8.5 Methods for statistical analyses

The primary analysis of the primary and key secondary endpoints will include all data captured during the 56-week treatment period, regardless of whether study treatment was prematurely discontinued, or delayed, and/or irrespective of protocol adherence.

Demography and baseline characteristics will be summarized by treatment group for the full analysis set. In the event that there are major differences between the full analysis set and safety analysis set, these summaries will also be repeated for the safety analysis set.

Testing strategy to account for multiplicity considerations

To account for multiplicity to test the primary (exacerbation) and two key secondary endpoints (FEV₁ and SGRQ) for each of the 30mg and 100mg dose groups (for subjects with baseline blood eosinophils $\geq 220/\mu\text{L}$) a testing strategy will be followed to control the overall type I error rate at level 0.05. The testing strategy will be according to the following gate keeping procedure:

Step 1: Perform the two tests of annual COPD exacerbation rate (one test for each dose vs. placebo) at the family wise error rate (FWER) of 0.04 using a Hochberg Procedure ([Hochberg](#))

[figure not shown]
1988). If both p-values are less than 0.04, then proceed to Step 2; else if the smaller p-value is less than 0.02 then proceed to Step 2a; otherwise no null hypothesis is rejected

Step 2: Test the two key secondary endpoints for both doses as one family at the FWER of 0.05 using a Holm Procedure (Holm 1979).

Step 2a: Test the two secondary endpoints for the smaller-p-value dose at the FWER of 0.01 using a Holm Procedure.

The gatekeeping procedure is also shown in the diagram below:

Figure 4 Gatekeeping Procedure

Since the correlation of the two test statistics for COPD exacerbation rate in the Step 1 is positive, the FWER of the Hochberg Procedure is strongly controlled at 0.04. The overall FWER of the gatekeeping procedure is strongly controlled at 0.05.

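### Does ending the FEV1 and SGRQ models at the EOT visit drop week-56 data from patients who stop treatment early?

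*Protocol*

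**What the plan says.** The protocol uses EOT for two different visits.

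- **Visit 19 at week 56.** The synopsis says: "The end of treatment (EOT) visit will occur at week 56". Table 3 puts the EOT label on Visit 19, week 56.
- **The discontinuation visit.** Section 3.6.1 says: "Subjects who prematurely discontinue treatment should return to the study centre and complete the procedures described for the EOT 12 weeks" after the last dose. The Table 3 footnote on telephone follow-up uses the same sense, with calls running "after the EOT visit up to week 56 as per the study plan".

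The statistical sections say:

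- Section 8.4.1, for all efficacy objectives, evaluates the 56-week treatment period, "defined as the period after administration of randomised investigational product at Visit 4 and the EOT at Visit 19, inclusive".
- Section 8.4.1.4 uses FEV1 change at each post-randomisation visit "up to and including the end of 56-week double-blind treatment visit (Visit 19) will be used as secondary efficacy variables".
- Section 8.4.3 defines the SGRQ comparison as change from baseline at week 56.
- Section 8.5, on the main analysis of the primary endpoint and both key secondary ones, says that it "will include all data captured during the 56-week treatment period, regardless of whether study treatment was prematurely discontinued".
- Section 8.5.2.1 sets the dependent variable of the FEV1 model as the change "at post-baseline protocol-specified visits (up to the EOT visit", with no visit number or week attached. SGRQ takes a similar model.

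**The concern.** FEV1 and SGRQ at week 56 are the two key secondary endpoints in the multiplicity procedure, so which observations enter their models should not be in doubt. The section describing the model stops at the EOT visit, and for an early stopper the protocol has its own EOT visit, clearly separate from week 56. If an analyst used that meaning, every later clinic value from an early stopper would be dropped, including the week-56 assessment that section 3.6.1 asks for. The analysis would then project on-treatment trajectories to week 56 under missing at random, a choice that tends to favour an active drug. It would no longer use the data collected after stopping, as section 8.5 requires.

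A second worry is that spirometry done at an early EOT visit might keep its EOT label and be entered as a week-56 value. The primary-endpoint text in section 8.4.1.1 ties EOT to Visit 19 and week 56 for exactly these patients. The sentence in section 8.5.2.1 does not, which makes the contrast look like a real gap.

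**Working it through.** **Step 1. What the discontinuation meaning would do.**

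Inputs:
- The dosing rule (every 4 weeks for three doses, then every 8 weeks, last at week 48) gives doses at weeks 0, 4, 8, 16, 24, 32, 40 and 48.
- The clinic schedule (section 4.2.1, Table 3) gives post-baseline FEV1 at weeks 4, 8, 16, 24, 32, 40, 48 and 56.
- Early EOT week = week of last dose + 12.

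| Last dose (week) | Early EOT (week) | FEV1 visits after it | FEV1 visits after last dose, kept |
|---|---|---|---|
| 0 | 12 | 16, 24, 32, 40, 48, 56 (6) | 4, 8 |
| 4 | 16 | 24, 32, 40, 48, 56 (5) | 8, 16 |
| 8 | 20 | 24, 32, 40, 48, 56 (5) | 16 |
| 16 | 28 | 32, 40, 48, 56 (4) | 24 |
| 24 | 36 | 40, 48, 56 (3) | 32 |
| 32 | 44 | 48, 56 (2) | 40 |
| 40 | 52 | 56 (1) | 48 |

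Under this meaning, 1 to 6 visits are lost, always including week 56. One or two visits after the last dose stay in the model even so.

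**Step 2. The possible size under that meaning.**

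Let d be the share who stop and D the on-treatment effect. Suppose the benefit has gone entirely by week 56 in those who stop. The effect regardless of discontinuation is then (1 − d)D. A truncated model that recovers D in full overstates it by D / [(1 − d)D] − 1 = d/(1 − d).

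- d = 0.10 (the dropout rate in section 8.2, borrowed as a stopping rate): 0.10/0.90 = 11%.
- d = 0.20 (an assumed upper value): 0.20/0.80 = 25%.

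These are extremes. Patients who leave the study have no week-56 value to discard. Under the second option in section 3.6.1 (telephone calls and eDiary only) no further spirometry or SGRQ is done, so again nothing can be discarded. Only stoppers who keep attending clinic matter, and the protocol gives no figure for them.

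**Step 3. Which meaning applies.**

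- Section 8.4.1 covers all efficacy objectives and names Visit 19 as the EOT that closes the period.
- Section 8.4.1.4 defines the very variable that section 8.5.2.1 models, and runs it through Visit 19.
- The SGRQ variable is fixed at week 56. The disputed phrase reaches it only by reference to a similar model.
- Section 8.5 names the key secondary endpoints when it includes data after discontinuation, and section 8.3.2 adds the intention-to-treat principle.
- Section 3.6.1 is a conduct section. It says when patients return and does not define an analysis cut-off.

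With EOT = Visit 19, the number of scheduled FEV1 visits excluded for an early stopper is 0 in every row of the table.

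**Step 4. The mislabelling route.**

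Six of the seven early EOT times (weeks 12, 20, 28, 36, 44 and 52) fall in telephone weeks and match no scheduled spirometry visit. Nothing in the protocol assigns them to week 56. Stoppers who keep attending have separate Visit 19 procedures at week 56. Assigning an off-schedule assessment to a visit window is ordinary content of a statistical analysis plan, which is not available here.

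**The case for a change.** The strongest argument for a change is that the model section decides what enters two multiplicity-controlled tests, and it is the one place where EOT carries neither a visit number nor a week. The discontinuation meaning is no stray usage: sections 3.6, 3.6.1 and 4.2.1 and a Table 3 footnote all rely on it. A programmer working from section 8.5.2.1 alone could choose it, and correcting the phrase would cost nothing.

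The double usage is real, and a visit number would have been tidier. The claimed contradiction does not survive, because the key secondary text does contain the qualifier: section 8.4.1.4 supplies it for FEV1 and section 8.4.3 for SGRQ. Choosing the discontinuation meaning would require the analyst to ignore both, along with section 8.4.1 and the explicit rule in section 8.5. A clearer label would therefore confirm the analysis already specified and alter none of it.

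**Conclusion.** The concern does not hold as a defect. Read within section 8, the FEV1 model runs through Visit 19 at week 56, SGRQ is assessed at week 56, and data collected after discontinuation are included for both. The loss of scheduled FEV1 visits is zero, and sample size, power and alpha are untouched. The 11% to 25% overstatement belongs to a reading that section 8 rules out. It also assumes that every stopper attends clinic at week 56, that no benefit remains, and that the truncated model recovers the full on-treatment effect. What is left is an abbreviation used in two senses, which analysts would resolve correctly from the definitions beside it. This conclusion assumes that visit windows for the early EOT assessment are set in the statistical analysis plan, as is usual.
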